5.2.11. Safety Analyses

5.2.11.1. Adverse Events

Adverse events will be listed by patient, system organ class, Medical Dictionary for Regulatory Activities® (MedDRA) preferred term, severity, and relationship to the study disease, drug, device, or procedure for all patients. Adverse events will be summarized as treatment-emergent adverse events (TEAEs) for the FAS population. Treatment-emergent adverse events are defined as events that are newly reported after first study treatment following randomization, or reported to worsen in severity from baseline. The proportion of patients experiencing each TEAE will be presented by preferred term, system organ class (SOC), and treatment group. The proportion of patients experiencing each TEAE that are assessed as possibly related to the study disease, drug, device, or procedures will also be summarized. The number and proportion of patients will be presented and compared by treatment using Fisher's exact test or Pearson's chi-square test for the FAS population. TEAEs will be summarized by preferred term within SOC and by preferred term by decreasing frequency.

All SAEs will be listed by patient and summarized by treatment as counts and percentages. If a sufficient number of SAEs are reported, the proportion of patients with SAEs between treatment groups will be compared using Fisher's exact test. Similar analyses will be performed for discontinuations due to AEs.

5.2.11.1.1. Special Topic Assessment of Allergic Events

The special topic assessment of allergic events will be performed by an initial blinded review of preferred terms (PTs) by SOC in order to identify all possible cases of allergic events, followed by a comparison between treatment arms. The goal of the initial blinded review, which will be carried out by the safety physician, is to identify all reported allergic reactions. As an initial reference for this blinded review, Lilly will consider the list of PTs shown in [Appendix 1](#). Justification in including or excluding events based on medical judgment and other supportive information will be provided when applicable. All allergic events will be listed by patient and summarized by treatment as counts and percentages. The proportion of patients with allergic reactions between treatment groups will be compared using Fisher's exact test or Pearson's chi-square test for the FAS.

5.2.11.1.2. Assessment of Injection Site Adverse Events

Whenever an injection site adverse event occurs, there is an evaluation of the pain, pruritus, and rash associated with the injection as well as of the characteristics of the injection site (abscess, nodule, lipoatrophy, lipohypertrophy, or induration). The proportion of patients experiencing injection site adverse events will be summarized and analyzed by treatment group. Additional analyses will be done as deemed appropriate.

5.2.11.2. Hypoglycemic Events

A **hypoglycemic episode** is that at any time a patient feels as he/she is experiencing a sign or symptom that is associated with hypoglycemia or has a BG level of ≤ 70 mg/dL (≤ 3.9 mmol/L), even if it was not associated with signs, symptoms, or treatment consistent with current guidelines (Seaquist et al. 2013).

Severe hypoglycemia: an event requiring assistance of another person to actively administer carbohydrates or glucagon or take other corrective actions. Plasma glucose concentrations may not be available during an event, but neurologic recovery following the return of plasma glucose to normal levels is considered sufficient evidence that the event was induced by low plasma glucose concentration. Sub-categories of severe hypoglycemia of primary interest are:

- **Severe hypoglycemia (BG level ≤ 70 mg/dL[3.9 mmol/L]):** severe hypoglycemia with accompanying BG level ≤ 70 mg/dL (3.9 mmol/L)
- **Severe hypoglycemia (not biochemically confirmed—BG missing):** severe hypoglycemia without an accompanying BG level (no BG level obtained prior to administration of treatment or at the time of neuroglycopenic symptoms)

- **Severe hypoglycemia (not biochemically confirmed—BG not aligned with severe symptoms):** severe hypoglycemia in which the event was reported/confirmed by the investigator as a severe hypoglycemic event associated with neuroglycopenic symptoms or cognitive impairment that required assistance for active administration of glucose or glucagon for recovery, but a BG level >70 mg/dL was reported on the case report form that cannot be resolved through queries.

Nocturnal hypoglycemia: any total hypoglycemic event that occurs after bedtime and prior to the first meal upon waking (eg, breakfast).

Nonnocturnal hypoglycemia: any event that occurs between waking and bedtime.

Documented symptomatic hypoglycemia: an event during which typical symptoms of hypoglycemia are accompanied by a measured plasma glucose concentration ≤ 70 mg/dL (≤ 3.9 mmol/L).

Asymptomatic hypoglycemia: an event not accompanied by typical symptoms of hypoglycemia but with a measured plasma glucose concentration ≤ 70 mg/dL (≤ 3.9 mmol/L).

Probable symptomatic hypoglycemia: an event during which symptoms typical of hypoglycemia are not accompanied by a plasma glucose determination but that was presumably caused by a plasma glucose concentration ≤ 70 mg/dL (≤ 3.9 mmol/L).

Pseudo-hypoglycemia: an event during which the person with diabetes reports any of the typical symptoms of hypoglycemia with a measured plasma glucose concentration >70 mg/dL (> 3.9 mmol/L) but approaching that level.

Besides the hypoglycemic categories listed above, total hypoglycemic event will be defined as follows:

Total hypoglycemic event: any event which is either documented symptomatic hypoglycemia, asymptomatic hypoglycemia, probable symptomatic hypoglycemia or severe hypoglycemia.

For each category of hypoglycemia event, the incidence, the number of hypoglycemic events per patient, the rate of hypoglycemic events per year (that is, the number of hypoglycemic episodes per patient per patient year [365.25 days]) will be calculated. These measures will be summarized at baseline, titration, maintenance, and overall study periods and at endpoint.

The proportion of patients with at least 1 hypoglycemic event (total, severe, nocturnal, and others) or incidence during the study will be summarized (counts and percentages) and analyzed using Fisher's exact test or the Pearson's chi-square test for the FAS population.

Logistic regression will be used as a sensitivity analysis of the incidence of hypoglycemia. The model will have presence or absence of hypoglycemia as the dependent or response variable and treatment, baseline HbA_{1c}, pre-study treatment (Lantus®-bolus, other basal-bolus, premixed insulin), and pre-study metformin or acarbose usage (metformin only, acarbose only, or neither) as the independent terms in the model.

The rate of hypoglycemic episodes per year (total, severe, nocturnal, and others) will be analyzed at baseline, titration, maintenance, and overall study periods and at endpoint using the Wilcoxon test. In addition, the hypoglycemia rates will also be analyzed using a negative binomial model for the FAS population with terms for treatment, baseline HbA_{1c}, pre-study treatment (Lantus®-bolus, other basal-bolus, premixed insulin), and pre-study metformin or acarbose usage (metformin only, acarbose only, or neither).

In addition, the total number of patients with at least 1 hypoglycemic episode divided by the total extent of exposure in patient-years will be calculated for the overall study period and summarized descriptively for each treatment group for total, severe, nocturnal, documented symptomatic, and asymptomatic hypoglycemia definitions only. Individual patient listing of hypoglycemic events by visit will be presented for the FAS population.

All the above analysis will be repeated with the threshold of **Clinically significant hypoglycemia**: <54 mg/dL (3.0 mmol/L).

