9.10. Hypoglycemic Episodes

Patients should check their BG level whenever possible if they have symptoms suggestive of hypoglycemia. For each hypoglycemic episode, patients should record their BG level, associated symptoms, and treatment in the study diaries provided by the sponsor via the investigator.

When instructing patients on recognition and management of hypoglycemic episodes, a **hypoglycemic episode** is defined as any time a patient feels that he/she is experiencing a sign or symptom that is associated with hypoglycemia or has a BG level ≤ 70 mg/dL (≤ 3.9 mmol/L), even if it was not associated with signs, symptoms, or treatment consistent with current guidelines (ADA 2005).

Note: Episodes of severe hypoglycemia should also be recorded as SAEs (Section 10.3.1.1).

Severe hypoglycemia: An event requiring assistance of another person to actively administer carbohydrate, glucagon, or other resuscitative actions. During these episodes, the subject has an altered mental status and cannot assist in his/her care, are semiconscious or unconscious, or experience coma with or without seizures, and may require parenteral therapy. Blood glucose measurements may not be available during such an event, but neurological recovery attributable to the restoration of BG concentration to normal is considered sufficient evidence that the event was induced by a low BG concentration (BG ≤ 70 mg/dL [3.9 mmol/L]).

Nocturnal hypoglycemia: Any hypoglycemic event that occurs between bedtime and waking.

Documented Hypoglycemia:

- **Documented symptomatic hypoglycemia:** An event during which typical symptoms of hypoglycemia are accompanied by plasma glucose (PG) ≤ 70 mg/dL (≤ 3.9 mmol/L).
- **Documented asymptomatic hypoglycemia:** An event not accompanied by typical symptoms of hypoglycemia but with PG ≤ 70 mg/dL (≤ 3.9 mmol/L).
- **Documented unspecified hypoglycemia:** An event during which PG ≤ 70 mg/dL (≤ 3.9 mmol/L) but no information relative to symptoms of hypoglycemia was recorded.

Probable symptomatic hypoglycemia: An event during which symptoms typical of hypoglycemia are not accompanied by a plasma glucose determination but that was presumably caused by a plasma glucose concentration ≤ 70 mg/dL (≤ 3.9 mmol/L).

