Relative hypoglycemia (also referred to as Pseudohypoglycemia): An event during which the person with diabetes reports any of the typical symptoms of hypoglycemia with a measured plasma glucose concentration >70 mg/dL (>3.9 mmol/L) but approaching that level.

Overall hypoglycemia: This optional category combines all cases of hypoglycemia (documented hypoglycemia and probable symptomatic hypoglycemia, including severe hypoglycemia) excluding the events of relative hypoglycemia. Nocturnal and severe hypoglycemia are special cases of documented or probable hypoglycemia. If an event of hypoglycemia falls into multiple subcategories, that event should only be counted once in this category.

10. Efficacy, Health Outcome/Quality of Life Measures, Safety Evaluations, Sample Collection and Testing, and Appropriateness of Measurements

Study procedures and their timing (including tolerance limits for timing) are summarized in the Study Schedule ([Attachment 1](#)).

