12.2.9.3. Hypoglycemic Events

The incidence, rate per 30 days and rate per year of hypoglycemic episodes (total, severe, and nocturnal as defined in Section 9.10) will be summarized by treatment at baseline, titration, maintenance, and overall study periods and at endpoint. The rate per 30 days between 2 visits is defined as the total number of episodes between the visits divided by the actual number of days between the visits, and then multiplied by 30 days.

The proportion of patients (with at least 1 hypoglycemic event (total, severe, nocturnal, and others) or incidence during the study will be summarized (counts and percentages) and analyzed using Fisher's exact test or the Pearson's chi-square test for the FAS population.

The rate of hypoglycemic episodes per 30 days and per year (total, severe, nocturnal, and others) will be analyzed at baseline, titration, maintenance, and overall study periods and at endpoint using the Wilcoxon test. In addition, the hypoglycemia rates will also be analyzed using a negative binomial model for the FAS population with terms for treatment, baseline HbA1c, prestudy treatment, and prestudy metformin or acarbose usage. The offset variables are log of patient's treatment duration/30 and log of patient's treatment duration/365.25 for the models analyzing hypoglycemia rate per 30 days and per year, respectively.

In addition, the total number of patients with at least 1 hypoglycemic episode divided by the total extent of exposure in patient-years will be calculated for the overall study period and summarized descriptively for each treatment group for total, severe, nocturnal, documented symptomatic, and asymptomatic hypoglycemia definitions only. Listings of hypoglycemic episodes will be presented by visit for each subject.

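### Read literally, the SAP's total hypoglycemia count omits the protocol's documented unspecified events (glucose at or below 70 mg/dL, symptoms not recorded), and nocturnal hypoglycemia inherits the gap

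*SAP*

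**What the plan says.** **Protocol, Section 9.10.** Documented hypoglycemia is divided into symptomatic, asymptomatic and unspecified events. Unspecified means a plasma glucose at or below 70 mg/dL "but no information relative to symptoms of hypoglycemia was recorded". A combined category named overall hypoglycemia, described as optional, "combines all cases of hypoglycemia (documented hypoglycemia and probable symptomatic hypoglycemia, including severe hypoglycemia) excluding the events of relative hypoglycemia". An event that fits several subcategories is counted once. Nocturnal hypoglycemia covers any hypoglycemic event between bedtime and waking.

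**Protocol, Section 12.2.9.3.** The events to be summarised are "total, severe, and nocturnal as defined in Section 9.10". Section 9.10 does not itself use the term total.

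**SAP, Section 5.2.11.2.** The SAP defines severe, nocturnal, nonnocturnal, documented symptomatic, asymptomatic, probable symptomatic and pseudo-hypoglycemia. It has no unspecified category. Asymptomatic hypoglycemia is "an event not accompanied by typical symptoms of hypoglycemia but with a measured plasma glucose concentration" at or below 70 mg/dL. A total event is "any event which is either documented symptomatic hypoglycemia, asymptomatic hypoglycemia, probable symptomatic hypoglycemia or severe hypoglycemia". Nocturnal hypoglycemia begins from total: "any total hypoglycemic event that occurs after bedtime" and before the first meal on waking.

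**Changes from the protocol.** Under SAP Section 5.2.1, a change in analysis method and its justification are to be described in the SAP and/or the clinical study report. The SAP gives no justification for this one.

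**The concern.** Hypoglycemia is one of three safety comparisons named in the secondary objectives, beside anti-glargine antibodies and injection-site reactions. Total and nocturnal hypoglycemia are two of the main ways it is analysed. If the SAP list is programmed as written, an event with a measured low glucose is dropped from both counts because its symptom status was not recorded.

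Such events are foreseeable. Patients take daily readings and repeated 4-point and 7-point profiles, including a 3 am value (Protocol Section 7.2.3). They enter symptoms in a diary themselves (Section 9.10). A low routine reading with no symptom entry is plausible, and the protocol has a category for it.

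The omission carries beyond the main table. Total or nocturnal events feed the incidence and rate analyses, the repeat at <54 mg/dL, the subgroup analyses (SAP Section 5.2.12) and the antibody analyses that use the total hypoglycemia rate (SAP Section 5.2.11.4).

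**Working it through.** The documents state no hypoglycemia rate, no share of events with symptoms unrecorded and no power for this comparison, so there is no plan figure to reproduce. The check is a comparison of definitions.

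**Step 1. Set the two combined counts side by side.**

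| Event type | Defined in Protocol 9.10 | Defined in SAP 5.2.11.2 | In protocol overall | In SAP total |
|---|---|---|---|---|
| Documented symptomatic | yes | yes | yes | yes |
| Asymptomatic, glucose ≤70 mg/dL | yes | yes | yes | yes |
| Documented unspecified | yes | no | yes | not listed |
| Probable symptomatic | yes | yes | yes | yes |
| Severe | yes | yes | yes | yes |
| Relative (pseudo-) hypoglycemia | yes | yes | no | no |

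The two counts differ in one row only.

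**Step 2. Trace a non-severe event with glucose ≤70 mg/dL and no symptom entry through the SAP.**
- It is not documented symptomatic, because no symptoms are recorded.
- It is not probable symptomatic, because that type has no glucose value.
- It is not asymptomatic on a literal reading, because that type requires symptoms to be absent, and the protocol keeps absent and unrecorded apart.
- It is therefore not total, and so cannot be nocturnal.

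**Step 3. Effect on rates (illustration; all shares assumed).** Let the true rates be equal in the two arms, and let u_T and u_R be the shares of events lost in the LY2963016 and Lantus arms.

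Observed rate ratio = (1 − u_T)/(1 − u_R)

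- Equal loss of 5%, 10% or 20%: the ratio is 1.00, and each arm's rate is understated by that share.
- 5% against 10%: 0.95/0.90 = 1.056.
- 5% against 15%: 0.95/0.85 = 1.118; reversed, 0.85/0.95 = 0.895.
- 10% against 20%: 0.90/0.80 = 1.125.

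**Step 4. How often such a ratio would reach nominal significance (illustration).** Take 129 patients per arm (SAP Section 5.1.1), an assumed mean of 20 events per patient and an assumed negative binomial dispersion k of 0.5 or 1.0.

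SE(log ratio) = √[2(k + 1/20)/129] = 0.092 or 0.128

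For a ratio of 1.118 (log = 0.111), the chance of two-sided p < 0.05 with equal true rates is 23% (k = 0.5) or 14% (k = 1.0), against 5% with no differential loss.

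With unspecified events restored to total, u = 0 from this cause in both arms and the ratio returns to 1.00.

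**The case against.** The strongest reply is that the text shows an unstated classification rule and not a demonstrated loss of events. A programmer might place blank symptom fields under asymptomatic, and total and nocturnal would then be complete. The case report form and the sponsor's unpublished white paper on hypoglycemia classification, listed in the SAP references, are not available. Data edits and queries could make blanks rare. This stands as a limit on size. It does not remove the point: the SAP states no such rule, and under it the asymptomatic category would no longer match the protocol's.

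The protocol anchor is also softer than it could be. Overall hypoglycemia is optional, and Section 9.10 defines no total. But the two wide definitions available there, hypoglycemic episode and overall hypoglycemia, both include unspecified events.

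A reader might infer several stronger things that the documents do not support:
- *That the event falls in no SAP category at all.* Nonnocturnal hypoglycemia takes in any event between waking and bedtime, so a daytime event fits there.
- *That the SAP contradicts its own opening definition*, which covers any glucose at or below 70 mg/dL "even if it was not associated with signs, symptoms, or treatment consistent with current guidelines". In both documents the general episode is wider than the combined count, since it also takes in symptoms with glucose above 70 mg/dL. A narrower total is not in itself a contradiction.
- *That the between-arm comparison is biased.* This needs recording to differ by arm, and nothing shows that. Nor is Lantus familiar to every patient: two of the three prestudy-treatment strata were not on it.
- *That the whole safety objective rests on an incomplete count.* Antibodies, injection-site reactions, and severe and documented symptomatic hypoglycemia are untouched.

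The fix would not make total independent of symptom recording either, because probable symptomatic events still rest on reported symptoms.

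**Conclusion.** The point holds as a mismatch of definitions. The SAP drops a category that the protocol names and counts, without a stated reason, and read literally this removes glucose-confirmed events from total and nocturnal hypoglycemia and from the analyses built on them.

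The size cannot be determined from the documents. Each arm's rate would be understated by its own share of unspecified events. The ratio would shift only if those shares differed, and it could shift either way. The ratios and significance chances shown above rest on assumed shares, event rate and dispersion; they illustrate the mechanism and are not estimates for this trial. In the incidence analyses, a patient changes status only if every qualifying event was unspecified.

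Hypoglycemia has no margin or decision rule, so the primary noninferiority conclusion is unaffected. The change should be made because it is cheap and restores agreement with the protocol, not because a bias has been shown.

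**What to change.** In SAP Section 5.2.11.2:
- restore documented unspecified hypoglycemia with the protocol definition, so that the classification of missing symptom status is explicit;
- define total as documented (symptomatic, asymptomatic or unspecified), probable symptomatic or severe, counting each event once;
- state that total corresponds to the protocol's overall hypoglycemia;
- report the number and rate of unspecified events by arm, so that any difference in recording is visible.

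Nocturnal hypoglycemia, the <54 mg/dL repeat, and the subgroup and antibody analyses then follow without further edits. The cost is a short SAP edit and a programming change, with no new data. It should be settled before database lock.

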7.2.2. Study Visits

7.2.2.1. Screening (Visit 1)

Approximately 2 weeks prior to the start of the study, all potential study patients eligible for randomization will be screened after signing the informed consent form (ICF) and will receive a patient number. The medical history and preexisting conditions, previous insulin exposure, physical examination, height, weight, vital signs, electrocardiogram (ECG) readings, concomitant medications, and adverse events will be recorded during this visit. Laboratory assessments will be performed to determine the eligibility of patients and to include pregnancy tests for women of child-bearing potential (performed at a central laboratory). The HbA1c, hematology and serum chemistry assays will be performed at a central laboratory ([Attachment 1](#) and [Attachment 2](#)). Serum pregnancy tests will be performed on all females of childbearing potential at Visit 1 and when clinically indicated. Urine pregnancy tests at other visits can be accepted per local regulations. A urine pregnancy test may be repeated locally for any visits if considered necessary by the investigators and/or in compliance with local regulations.

Each patient will be given a glucometer (and associated supplies) and will be trained on its use in monitoring their BG levels during the study (Section 7.2.3), including instructions on obtaining the 7-point SMBG profiles that will be collected at Visit 2. Qualified medical staff will instruct patients about signs and symptoms of hypoglycemia and hyperglycemia and how to manage them. Patients will be provided study diaries and training to properly use the study diary at Visit 1 for recording BG values, corresponding insulin doses, hypoglycemic episodes, any AEs, and concomitant medications taken during the study ([Attachment 1](#)). If allowed by local law, patients may keep the study-provided blood glucose meter at the end of their study participation.

Patients who do not meet all the inclusion criteria at Visit 1 will be considered screen failures. As the patient's eligibility for randomization may not be known at Visit 1 (for example, given that results of laboratory tests may not be available), the site could either provide a tentative schedule for Visit 2 or arrange for follow up with the patient to confirm eligibility, and then prepare for and schedule Visit 2 as they deem appropriate and efficient.

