7.2.2.2. Randomization (Visit 2)

7.2.2.2.1. Patients Eligible for Randomization at Visit 2

At Visit 2, additional clinical assessments will occur, as outlined in the Study Schedule ([Attachment 1](#)). More specifically, the following activities will also occur at this visit:

- Eligible patients will be randomized to 1 of 2 treatment groups by a random assignment based on Visit 1 HbA1c, prestudy treatment with basal-bolus insulin or premixed insulin, and prestudy metformin or acarbose usage (metformin only, acarbose only, or neither). For patients with prestudy treatment of metformin or acarbose (excluding those taken both) prior to Visit 1, their concomitant OAM will be discontinued at Visit 2.
- Study material (study insulins, diary, and blood glucose monitoring supplies) will be dispensed or distributed at Visit 2 as indicated in the Study Schedule ([Attachment 1](#)).
- Study personnel will train patients on insulin pen injector use and proper injection technique, SMBG levels (Section 7.2.3), and proper use of the study diary for recording AEs, BG values and corresponding insulin doses, and hypoglycemia recognition and management.
- Patients also will be instructed about diet and physical activity and encouraged to maintain healthful habits of diet/activity throughout the study.
- Study diaries from Visit 1 will be collected, and patients will be given a study diary at Visit 2 and each subsequent investigator-site visit. The diaries will be source documents for the patients with records of BG levels, insulin doses, and episodes of hypoglycemia that occur throughout the study. The diaries will be collected at each subsequent investigator-site visit to transfer data, and will be used by the investigator to determine any dose adjustments needed for a patient. As indicated in the Study Schedule ([Attachment 1](#)), baseline 7-point SMBG profiles will also be reviewed and transferred to an electronic case report form (eCRF).
- Patient safety will be assessed, including body weight, vital signs, use of concomitant medications, and any AEs or hypoglycemic episodes that occurred since Visit 1.
- A blood sample will be drawn to determine the baseline HbA1c level. Blood samples will be drawn during Visit 2 for immunogenicity tests and biomarker detection (as warranted) (Section 10.4.2). Patients will be administered questionnaires (ITSQ) to assess PROs at baseline with regard to insulin treatment satisfaction.

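### The negative binomial model for hypoglycemia rates leaves out each patient's own baseline rate, which costs precision but not validity, and perhaps not much precision

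*SAP*

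**What the plan says.** Both documents specify the same model. SAP 5.2.11.2 says that "the hypoglycemia rates will also be analyzed using a negative binomial model for the FAS population", and adjusts the treatment comparison for baseline HbA1c, pre-study insulin regimen and metformin or acarbose use. Protocol 12.2.9.3 has a "negative binomial model for the FAS population with terms for treatment, baseline HbA1c, prestudy treatment, and prestudy metformin or acarbose usage", and adds the exposure terms: "The offset variables are log of patient's treatment duration/30 and log of patient's treatment duration/365.25". Neither lists a baseline hypoglycemia rate, and neither gives a reason for leaving it out.

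The information is collected. Protocol 7.2.2.1 places screening "Approximately 2 weeks prior to the start of the study"; patients receive the meter, diary and hypoglycemia training at that visit. Under Protocol 7.2.2.2, the Visit 2 safety review covers "any AEs or hypoglycemic episodes that occurred since Visit 1". The baseline rate is also derived, because SAP 5.2.11.2 says that the rate "will be analyzed at baseline, titration, maintenance, and overall study periods and at endpoint using the Wilcoxon test".

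The model supplements other analyses. Incidence is compared by Fisher's exact or chi-square test, with logistic regression as a sensitivity analysis, and the rate by Wilcoxon. In SAP 4.2, hypoglycemia is one of three items in a single secondary safety objective, beside anti-glargine antibodies and injection site reactions.

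**The concern.** Patients with type 1 diabetes may differ widely in how often they have low readings. If part of that difference persists from screening into treatment, a model without the baseline rate leaves it in the dispersion parameter, and the confidence interval for the rate ratio is wider than it needs to be. The negative binomial model is the only planned analysis in the hypoglycemia section that yields a covariate-adjusted rate ratio, so it is where added precision would be useful.

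The plan also tests the baseline rate between arms without saying how the result would be used. If a chance imbalance appeared, any adjustment for it would be post hoc.

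Elsewhere the SAP often does adjust for the baseline of the response: the continuous variables listed in SAP 5.2.1, the laboratory measures in 5.2.11.3 and the vital signs in 5.2.11.5. The hypoglycemia model keeps baseline HbA1c but not the baseline of its own outcome.

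**Working it through.** **The plan's own figure.** The only sample-size calculation is for HbA1c (Protocol 12.1, SAP 5.1.1): n per arm = 2 × 1.05² × (1.960 + 0.842)² / 0.40² = 108.2, rounded up to 109. With 15% dropout, 109 / 0.85 = 128.2, rounded up to 129. Power with 109 per arm is 80.3%. These agree with the documents. No rate, dispersion or precision is stated for hypoglycemia, so everything below on total events rests on assumptions.

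**Simulation for total hypoglycemia.** Taken from the documents: 129 per arm, 24 weeks of treatment, a baseline window of about 2 weeks. Assumed: 10, 40 or 80 events per patient-year; dispersion 0.8 or 1.5; correlation between baseline and on-treatment gamma frailties (set on the normal scale of a Gaussian copula) of 0, 0.3, 0.6 or 0.9; no treatment effect; no dropout. Model A has treatment and the log-time offset. Model B adds log((baseline count + 0.5) / baseline time). The planned HbA1c and stratum terms are in neither model. There were 60 runs per cell, and the entry is 1 − (SE_B / SE_A)², using median model-based standard errors.

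| Events per year | Dispersion | Corr. 0 | Corr. 0.3 | Corr. 0.6 | Corr. 0.9 |
|---|---|---|---|---|---|
| 10 | 0.8 | 0.0% | 1.1% | 6.0% | 9.1% |
| 10 | 1.5 | −0.1% | 0.3% | 7.5% | 16.4% |
| 40 | 0.8 | −0.3% | 3.2% | 12.2% | 29.3% |
| 40 | 1.5 | 0.1% | 3.2% | 12.3% | 34.5% |
| 80 | 0.8 | −0.6% | 4.4% | 16.8% | 43.5% |
| 80 | 1.5 | −0.8% | 2.8% | 17.7% | 45.4% |

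**What this means for the interval.** At 40 per year, dispersion 1.5 and correlation 0.6, the SE falls from 0.154 to 0.144. The 95% limits go from the estimate times or divided by exp(1.96 × 0.154) = 1.35 to exp(1.96 × 0.144) = 1.33. On the log scale the interval narrows by 1 − √(1 − 0.123) = 6%. In the most favorable cell it narrows by 1 − √(1 − 0.454) = 26%.

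**Severe hypoglycemia.** Protocol section 5 reports severe hypoglycemia as an SAE in 4.5% and 4.9% of patients over 52 weeks in the earlier type 1 study. With constant hazard, the chance of an event in 2 weeks is 1 − (1 − p)^(2/52), which is 0.00177 and 0.00193. Times 258, that is 0.46 and 0.50 patients. The baseline severe rate would be zero for almost everyone. A simulated severe scenario (assumed 0.1 events per year, dispersion 3, correlation 0.6) showed a 0% reduction, though only 22 of 60 runs gave usable fits.

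**The case against.** The strongest reply is that nothing here is wrong. Protocol and SAP agree, the comparison is randomized, and a model without this covariate is valid. That stands.

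The gain may also be small. Visit 1 has a 7-day allowance either way (Protocol Attachment 1), so the window may run from about 7 to 21 days. At an assumed 20 events per year, 14 days give 20 × 14 / 365.25 = 0.77 expected events; with dispersion 1.0, 1 / (1 + 0.77) = 57% of patients would score zero. The baseline reflects a different state: the pre-study insulin regimen, sometimes with metformin or acarbose, before conversion and titration. Capture of asymptomatic low readings may differ as well, since the scheduled 4-point profiles and weekly contacts start only after randomization. All this argues for a lower correlation, and it stands as a limit on size. The simulations include the counting noise of a 2-week window and still show gains at 0.6 and above. They omit the planned covariates, so the added gain could be overstated.

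Three stronger readings are tempting, and the documents do not support them:

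- A reader might infer that the trial's main safety comparison is weakened. The model supplements the Wilcoxon test and serves one of three items in a secondary objective.
- A reader might infer that the SAP breaks its own rule. The rule in SAP 5.2.1 names SMBG, weight, dose and vital signs, analyzed by MMRM; event counts are not on that list. The treatment-satisfaction ANCOVA in 5.2.10.1 also adjusts for baseline HbA1c and not for its own baseline.
- A reader might infer that the open-label design makes baseline imbalance a source of bias. Episodes before Visit 2 precede assignment, and any imbalance in them is due to chance.

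**Conclusion.** The omission is real in both documents and unexplained, and the covariate is already collected and derived. Its cost is precision alone, in a supplementary analysis of a named secondary safety outcome. Over assumed rates of 10 to 80 per patient-year and dispersions of 0.8 to 1.5, the avoidable share of the variance of the log rate ratio is about 0% to 4% at correlation 0 to 0.3, 6% to 18% at 0.6 and 9% to 45% at 0.9. The documents do not show which correlation applies, so a claim that close to half the variance is being wasted would rest on the most favorable cells alone. For severe events there is nothing to gain. Only total events were simulated; extending the result to nocturnal and documented symptomatic events, which are subsets and so rarer, is a judgment. This is a cheap improvement, not a defect that threatens the trial's conclusions.

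**What to change.** Before database lock, and before any interim look by treatment group, amend SAP 5.2.11.2 as follows:

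- Add log((episodes from Visit 1 to Visit 2 + 0.5) / days from Visit 1 to Visit 2) as a covariate in the negative binomial model for total hypoglycemia.
- Do the same for nocturnal and documented symptomatic hypoglycemia, each with its own baseline count, if pooled data without treatment codes show that those counts are not nearly all zero. State the threshold in advance.
- State a rule for patients with no usable baseline record, so that they are not silently dropped from the model.
- Leave the severe-event model as it is.

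If the sponsor prefers to keep the present model, the adjusted version can be prespecified as a sensitivity analysis. The cost is a few lines in the SAP and one derived variable, with no new data collection. The downside is that a covariate from about 2 weeks on the pre-study regimen is noisy, so the gain may turn out small.
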